## **12.6 Audits and Inspections**

The study may be audited at any time, with appropriate notification, by qualified personnel from the Sponsor or its designees, to assess compliance with the protocol, GCP and regulatory requirements. These audits may also be conducted for quality assurance to ensure that complete and accurate data are submitted and that adverse events, complications and/or adverse reactions are being identified and reported.

The study may also be inspected by health authority inspectors, after appropriate notification. In the event of an audit or an inspection, the Investigator must ensure that direct access to all study documentation, including source documents, is granted to the auditors or inspectors.

## **14.0 ETHICAL AND LEGAL CONSIDERATIONS**

This study will be conducted in accordance with the Declaration of Helsinki and in compliance with all applicable laws and regulations of the locale where the study is conducted.

It is the responsibility of the investigator that the patient is made aware and consent is given that personal information may be scrutinized during audits by competent authorities and properly authorized persons, but that personal information will be treated as strictly confidential and not be publicly available. The investigator is responsible for the retention of the patient log and patient records.

**APPENDIX I – PATIENT MEDICATION DIARY - BINIMETINIB**  
 (Binimetinib twice daily, every day in 28-day cycles)

Patient Name \_\_\_\_\_ Patient Study ID \_\_\_\_\_ Cycle # \_\_\_\_\_

**INSTRUCTIONS TO THE PATIENT:**

1. You will take **Binimetinib** \_\_\_\_\_ mg (\_\_\_\_ tablets) **twice per day on Days 1- 28 of every 28-day cycle**. Take doses about 12 hours apart at approximately the same times each day. You may take binimetinib with or without a meal. Tablets should be swallowed whole, do not chew or crush.
2. Record the date and the time you took each **Binimetinib** dose.  
 Record missed or skipped dose(s). If you miss a dose you may make up that dose if you take it within 6 hours of the time you normally take it. There must be at least 6 hours before the next dose.  
 If you vomit a dose, do not re-take the study drug. Take the next dose at the time that you normally take the next scheduled dose.
3. Bring this form and any remaining **Binimetinib** tablets when you return for each appointment.

Week	Day	Date	Time of morning dose	# of 15 mg tablets	Time of evening dose	# of 15 mg tablets	Comments
1	1						
	2						
	3						
	4						
	5						
	6						
	7						
2	8						
	9						
	10						
	11						
	12						
	13						
	14						
3	15						
	16						
	17						
	18						
	19						
	20						
	21						
4	22						
	23						
	24						
	25						
	26						
	27						
	28						

Patient's Signature \_\_\_\_\_ Date \_\_\_\_\_

Nurse's Signature \_\_\_\_\_ Date \_\_\_\_\_

## APPENDIX II – PATIENT MEDICATION DIARY - ENCORAFENIB

(Encorafenib once every day in 28-day cycles)

Patient Name \_\_\_\_\_ Patient Study ID \_\_\_\_\_ Cycle # \_\_\_\_\_

**INSTRUCTIONS TO THE PATIENT:**

1. You will take **Encorafenib** \_\_\_\_\_ mg (\_\_\_ capsules) **once daily on Days 1- 28 (daily) of every 28-day cycle.** Take Encorafenib with one of your daily doses of Binimetinib. **Encorafenib** may be taken with or without a meal. Capsules should be swallowed whole, do not open or crush.
2. Record the date and the time you took each **Encorafenib** dose.  
Record missed or skipped dose(s). If you miss a dose you may make up that dose if you take it within 12 hours of the time you normally take it. There must be at least 12 hours before the next dose.  
If you vomit a dose, do not re-take the study drug. Take the next dose at the time that you normally take the next scheduled dose.
3. Bring this form and any remaining **Encorafenib** tablets when you return for each appointment.

Week	Day	Date	Time of dose	# of 75 mg capsules	Week	Day	Date	Time of dose	# 75 of mg capsules
1	1				3	15			
	2					16			
	3					17			
	4					18			
	5					19			
	6					20			
	7					21			
2	8				4	22			
	9					23			
	10					24			
	11					25			
	12					26			
	13					27			
	14					28			

Patient's Signature \_\_\_\_\_ Date \_\_\_\_\_

Nurse's Signature \_\_\_\_\_ Date \_\_\_\_\_

### APPENDIX III – PRE-SURGICAL TREATMENT MEDICATION DIARY

Encorafenib (once daily) and Binimetinib (twice daily) for 10-14 days prior to surgery.

**Patient Name** \_\_\_\_\_

**Patient Study ID** \_\_\_\_\_

**INSTRUCTIONS TO THE PATIENT:**

1. You will take **Encorafenib** \_\_\_\_\_ mg (\_\_\_ capsules) every day in the morning starting 10-14 days prior to surgery. Also take encorafenib 2 hours before your scheduled surgery with a small amount of water.
2. You will take **Binimetinib** \_\_\_\_\_ mg (\_\_\_ tablets) twice per day starting 10-14 days prior to surgery. Also take binimetinib 2 hours before your scheduled surgery with a small amount of water.
3. **Encorafenib** and **Binimetinib** may each be taken with or without a meal. Pills should be swallowed whole, do not chew or crush. Encorafenib can be taken at the same time as binimetinib. If you miss a dose of encorafenib you may make up that dose if you take it within 12 hours of the time you normally take it. There must be at least 12 hours before the next dose of encorafenib. If you miss a dose of binimetinib you may make up that dose if you take it within 6 hours of the time you normally take it. There must be at least 6 hours before the next dose of binimetinib. If you vomit a dose of either study drug, do not re-take the study drug. Take the next dose of each study drug at the time that you normally take the next scheduled dose.
4. Record the date and the time you took each **Encorafenib** or **Binimetinib** dose and the number of pills you took. Record any missed or skipped dose(s). If you vomit a dose, do not re-take the study drug.
5. Bring this form and any remaining **Encorafenib** and **Binimetinib** pills when you return for each surgery.

Day	Date	Timeframe	Time of Dose	# pills of binimetinib	# pills of encorafenib	Comments
13 days prior to surgery		Morning				
		Evening			---	
12 days prior to surgery		Morning				
		Evening			---	
11 days prior to surgery		Morning				
		Evening			---	
10 days prior to surgery		Morning				
		Evening			---	
9 days prior to surgery		Morning				
		Evening			---	
8 days prior to surgery		Morning				
		Evening			---	
7 days prior to surgery		Morning				
		Evening			---	
6 days prior to surgery		Morning				
		Evening			---	
5 days prior to surgery		Morning				
		Evening			---	
4 days prior to surgery		Morning				
		Evening			---	
3 days prior to surgery		Morning				
		Evening			---	
2 days prior to surgery		Morning				
		Evening			---	
1 days prior to surgery		Morning				
		Evening			---	
(add'l day if surgery delayed)		Morning				
		Evening			---	
(add'l day if surgery delayed)		Morning				
		Evening			---	
Day of Surgery: 2 hours prior to surgery		Morning				
		Evening			---	

**Patient's Signature** \_\_\_\_\_ **Date** \_\_\_\_\_

**Nurse's Signature** \_\_\_\_\_ **Date** \_\_\_\_\_

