## Surgical Arm Treatment Schema

Subjects in the surgical cohort must be candidates for a clinically-indicated surgery and must have a BRAF V600E/K-mutated high-grade glioma or a low-grade glioma with high clinical suspicion for progression to high-grade. These subjects will take encorafenib and binimetinib in combination at their FDA-approved doses (see Section 4.3 for administration details) for 10-14 days prior to surgery, with a preference for 14 days, though a minimum of 10 days is acceptable. The last dose of both drugs will be administered two hours prior to surgery. Specimens will be collected as described in Section 9.6 and processed as described in the **Laboratory Manual**.

After surgery, the subjects will not take further encorafenib or binimetinib until a study visit to assess their neurological exam, physical exam (or telemedicine physical evaluation), and performance status, at 2-6 weeks post-operatively. At time of restarting combination treatment, subjects will follow the schedule listed above for the medical cohort, and will continue treatment as defined in Section 10.1.

Patients with histopathology inconsistent with high-grade glioma (either treatment effect or low grade glioma) will be replaced. Overall survival will be assessed from the first day that patient receives drug to death from any cause.

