### **4.3 Encorafenib and Binimetinib Administration**

Encorafenib will be administered in combination with binimetinib using the FDA approved doses. The dose of encorafenib is 450 mg orally once daily, taken with binimetinib. The dose of binimetinib is 45 mg orally twice daily, taken approximately 12 hours apart. It is recommended that both study drugs be taken in the morning rather than the evening. The study drugs may be taken with or without a meal.

Medical Arm patients: Encorafenib and binimetinib are taken every day for each 28 day cycle.

Surgical Arm patients: Encorafenib and binimetinib are taken for 10-14 days prior to surgery (preferably 14 days, though a minimum of 10 days is acceptable). The last dose of both drugs will be taken two hours prior to surgery. Following recovery from surgical resection (2-6 weeks), encorafenib and binimetinib are taken every day for each 28 day cycle.

If a subject vomits after taking study medication, the subject should be instructed not to retake the dose and should take the next dose as originally scheduled.

If a subject misses a dose of binimetinib, the subject may take the dose immediately if the next dose is scheduled for at least 6 hours later. If the next scheduled dose of binimetinib

is due in less than 6 hours, the subject should skip the dose and resume binimetinib dosing at the next scheduled dose.

If a subject misses a dose of encorafenib, the subject may take the dose immediately if the next dose is scheduled for at least 12 hours later. If the next scheduled dose of encorafenib is due in less than 12 hours, the subject should skip the dose and resume encorafenib dosing at the next scheduled dose.

Treatment will generally be administered on an outpatient basis. Patients will be provided with medication diaries ([Appendix I-IV](#)) and instructed in their use. Patients will be instructed to bring all unused medication and their diaries to each study visit for assessment of compliance.

Because study treatment is intended for self-administration, if coming to the clinic presents a safety risk, it is permitted to ship the study drug and the appropriate medication diaries to the patient's residence before the scheduled cycle Day 1. The study drug should be shipped by a secure delivery method with package tracking and a delivery confirmation. The regulatory requirements for maintaining investigational product remain and should be addressed and documented.

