Medical Arm and Surgical Arm (Post-Surgery): Encorafenib is administered orally once daily on Days 1-28 of each 28-day cycle (see Section [4.3](#)). Patients are required to keep a medication diary ([Appendix II](#)).
- 7 – Surgical Arm: Pre-surgery, Binimetinib is administered orally twice daily for 10-14 days prior to scheduled surgery, including the day of surgery (see Section [4.3](#)). Patients are required to keep a medication diary ([Appendix III](#)).  
Medical Arm and Surgical Arm (Post-Surgery): Binimetinib is administered orally twice daily on Days 1-28 of each 28-day cycle (see Section [4.3](#)). Patients are required to keep a medication diary ([Appendix I](#)).
- 8 – Evaluations done within +7 days of off treatment date unless indicated: do not repeat: if MRI within minus 14 days of off-treatment date; if H&P/neuro, KPS, labs within minus 5 days of off-treatment date.
- 9 – Adverse Events must be followed for at least 30 days from last dose of encorafenib and binimetinib.
- 10 – Perform within +14 days of the 30-day post-last dose date.
- 11 – Research blood for circulating tumor DNA (20 mL whole blood per time point) is to be collected at baseline, pre-Cycle 3, pre-Cycle 7, and at time of progression or off treatment. See Section [9.6.4](#).
- 12 – NA
- 13 – MRI with tumor measurements should be repeated every 8 weeks. See Section [4.1](#).
- 14 – Archived tumor tissue from the most recent tumor resection will be collected from patients when sufficient tissue is available. See Section [9.6.6](#).
- 15 – Surgical Arm: CSF will be collected during surgical procedure (required), prior to tumor disturbance. See Table [9.2.1](#) below and Section [9.6.4](#).  
CSF donation at the following time points is optional in Medical Arm and Surgical Arm patients and requires additional, specific consent on consent form. In patients who consent, it should be collected at baseline, prior to cycle 3, prior to cycle 7, and at progression (6 mL per time point) or off treatment. It can be collected via Ommaya reservoir or lumbar puncture. See Section [9.6.4](#).
- 16 – ECG should be done prior to study enrollment, then as indicated clinically.
- 17 – Echocardiogram or MUGA scan should be performed prior to study enrollment, prior to Cycle 2, then every 3 cycles (i.e. cycle 5, 8, 11 etc..) thereafter unless indicated more frequently

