## 9.2 Table of Additional Required Observations - Surgical Arm

Patients on the surgical arm will be required to undergo all baseline observations as detailed for the medical arm in Section [9.1](#) prior to surgical resection with the exception of research CSF collection. Upon resumption of encorafenib and binimetinib after surgery (as detailed in Section [4.1](#)), the Cycle 1-12 observations and off-treatment observations as detailed in the medical arm will also be observed. Observations listed below are additional on day of surgery.

Patients on the Medical Arm undergoing a clinically-indicated surgery for their brain tumor while on study should also adhere to specimen collection guidelines for Surgical Arm patients (below).

**Table 9.2** Required Observations on Day of Surgery – surgical arm patients

	Means of Collection	2 hours prior to surgery	Just prior to surgery (after induction of anesthesia)	Prior to tumor disturbance	During surgical resection	After closure
Encorafenib		1, 2				
Binimetinib		1, 2				
Blood	PD/Resistance/Circulating Tumor DNA: 10mL x 1		2,3			
	cTDNA:EDTA Lavender top 10mL x 2		2,3			
	PK: EDTA Lavender top 10mL x 1		2,3			2,3
Cerebrospinal Fluid	sterile container, 6mL			2,3		
Tumor Tissue	0.05-0.10 cm  contrast enhancing tumor				2,4	
	0.05-0.10 cm  non-enhancing tumor				2,4	
	0.5 cm  contrast enhancing tumor tissue				2,4	
	20 unstained slides					5
Documentation	On CRFs	2	2	2	2	2

- 1 – Encorafenib and Binimetinib should both be administered orally with a small quantity of water as necessary 2 hours before the patient’s surgical time.
- 2 – Exact time for all drug administration and sample removal should be charted on case report forms (CRFs).
- 3 – The blood and CSF samples should be collected as close in time to the resection as possible. In the event that a specific blood tube is not available, a reasonable substitution (in volume only) may be made; however, the blood collected should not exceed that as outlined in the consent document. The same tube-type should be collected in all instances (e.g., two 6mL lavender top / EDTA tubes may be substituted for a 10mL tube).
- 4 – Three surgical specimens should be removed and flash-frozen. See Section [9.6.5](#).
- 5 - 20 unstained FFPE slides should be requested after tissue specimen is processed and final pathology report is complete. See Section [9.6.5](#). This is in addition to archival tumor tissue obtained for all study patients.

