	Alopecia		Alopecia (Gr 2)
	Dry skin		Dry skin (Gr 2)
	Pruritus		Pruritus (Gr 2)
Rash acneiform			Rash acneiform (Gr 2)
Rash 			Rash (Gr 2)
	Skin and subcutaneous tissue disorders - Other (nail disorders)		
		Skin and subcutaneous tissue disorders - Other (severe cutaneous reaction) 	

Adverse Events with Possible Relationship to Binimetinib (CTCAE 5.0 Term) [n= 1374]			Specific Protocol Exceptions to Expedited Reporting (SPEER)
Likely (>20%)	Less Likely (<=20%)	Rare but Serious (<3%)	
	Skin and subcutaneous tissue disorders - Other (skin fissures)		
VASCULAR DISORDERS			
	Hypertension		Hypertension (Gr 2)
	Thromboembolic event		
	Vascular disorders - Other (hemorrhage) 		

This table will be updated as the toxicity profile of the agent is revised. Updates will be distributed to all Principal Investigators at the time of revision. The current version can be obtained by contacting [[contact]](mailto:[contact]). Your name, the name of the investigator, the protocol and the agent should be included in the e-mail.

Visual disorders may include visual disturbance, blurred vision, visual acuity reduced, flashing light, and floaters.

Retinopathy may include chorioretinopathy, chorioretinitis, and retinal detachment.

CPK increased may be associated with muscle pain and muscle weakness.

Rash may include rash maculo-papular and erythematous rash.

Severe cutaneous reactions may include bullous dermatitis, exfoliative dermatitis, erythema multiforme, and toxic skin eruptions.

The majority of hemorrhage events were mild, although serious bleeding events in the eyes, GI tracts or lungs have rarely been reported.

**Adverse events reported on binimetinib trials, but for which there is insufficient evidence to suggest that there was a reasonable possibility that binimetinib caused the adverse event:**

**Blood and lymphatic system disorders** - Febrile neutropenia

**Cardiac disorders** - Atrial fibrillation; Atrial flutter; Atrioventricular block complete; Cardiac arrest; Cardiac disorders - Other (atrioventricular block); Cardiac disorders - Other (irregular heart rate); Cardiac disorders - Other (tachyarrhythmia); Cardiac disorders - Other (tachycardia); Myocardial infarction; Palpitations; Supraventricular tachycardia

**Endocrine disorders** - Hypothyroidism

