### 9.6.5 Overview of Biospecimen Collection on Surgical Arm

Patients with a history of BRAF-V600E/K mutated glioma who are planning to undergo surgical tumor resection and are eligible to participate in this study (based on inclusion/exclusion criteria in Sections [3.2](#) and [3.3](#)) may participate in the surgical arm. Patients on the medical arm who experience likely progression and require a clinically indicated surgery are also eligible if they continue drug until the day of surgery. All patients in this cohort should take their last dose of binimetinib and encorafenib two hours prior to surgery. At the time of this clinically indicated surgery, biospecimens will be collected, after the induction of general anesthesia, in the following order:

- 1) Prior to tumor manipulation: Whole blood (total of 40 mL) and cerebrospinal fluid (6 mL).
  - a. Blood will typically be obtained from an arterial line and/or venous line placed as part of standard of care, placed immediately on wet ice, and processed as described in the **Laboratory Manual**.

- b. CSF will be obtained in one of three ways per discretion of the neurosurgeon ± principal investigator, placed immediately on wet ice, and processed as described in the **Laboratory Manual**. Determination as to the method of CSF extraction (specifically, whether or not a lumbar puncture is indicated) will be determined prior to surgery and patient will confirm on consent form.
    - i. By Ommaya reservoir access prior to the surgical procedure.
    - ii. By lumbar puncture after the induction of anesthesia so as to induce no additional discomfort to the patient.
    - iii. During surgery, from cisternal aspiration, if the cistern were to be opened as part of the planned surgical procedure.
    - iv. During surgery, from ventricular aspiration, if the ventricle were to be encountered as part of the planned surgical procedure.
- 2) At tumor manipulation: Enhancing and non-enhancing brain tumor tissue.
- a. After frozen section confirmation of glioma and confirmation with the pathologist that sufficient material has been obtained for clinical diagnostic processing (grading, sub classification, and the relevant genetic testing), additional tumor specimens will be obtained for this study and processed as described in the **Laboratory Manual**.

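### The pre-surgical diary leaves room for an evening binimetinib dose on the day of surgery, and Table 9.1 footnote 7 does not limit that day to one dose, although the protocol makes the dose two hours before surgery the last

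*Combined protocol and SAP*

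**What the plan says.** The rule itself is clear and repeated. Section 4.3: "The last dose of both drugs will be taken two hours prior to surgery". Section 9.6.5: "All patients in this cohort should take their last dose of binimetinib and encorafenib two hours prior to surgery". The surgical arm schema in Section 4.1 states the same rule and adds the hold: "After surgery, the subjects will not take further encorafenib or binimetinib until a study visit", which takes place 2-6 weeks after the operation. Table 9.2 enters both drugs only in the column two hours before surgery, and its footnote 1 agrees: "Encorafenib and Binimetinib should both be administered orally with a small quantity of water as necessary 2 hours before".

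Two other places handle the same day differently.

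- **Appendix III diary.** The last row is labelled "Day of Surgery: 2 hours prior to surgery" and has a morning and an evening line. On the evening line the encorafenib cell is struck out and the binimetinib cell is blank. Instruction 2 sets twice-daily binimetinib with a starting point but no stopping point, and then says: "Also take binimetinib 2 hours before your scheduled surgery with a small amount of water".
- **Table 9.1, footnote 7**, which the table cites in its day-of-surgery column: "Surgical Arm: Pre-surgery, Binimetinib is administered orally twice daily for 10-14 days prior to scheduled surgery, including the day of surgery". It refers the reader to Section 4.3.

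**The concern.** The diary is the form the patient doses from. On the day of surgery it looks like any other twice-daily day, and it does not say that the two-hour dose is the last. Instruction 2 presents that dose as an addition to the twice-daily schedule, not as its end. Instruction 3 sends a patient who has vomited a dose on to the next scheduled one, with no exception for this day. Footnote 7 leaves site staff with the same gap.

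Two things are at stake. The first is safety: the protocol holds both drugs after brain surgery, and its binimetinib risk list (Table 9-4) includes thromboembolic events and hemorrhage. On hemorrhage the table notes: "The majority of hemorrhage events were mild, although serious bleeding events in the eyes, GI tracts or lungs have rarely been reported". The second is the dosing record: instruction 4 asks patients to record missed or skipped doses, so a patient who stops correctly can appear to have missed one.

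**Working it through.** The plan gives no figure to reproduce here. The check is a comparison of texts and a dose count.

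**Step 1. Binimetinib doses on the day of surgery, by source**

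| Source | Doses on the day of surgery |
|---|---|
| Sections 4.1, 4.3, 9.6.5 | 1, two hours before surgery, then none until the 2-6 week visit |
| Table 9.2 | 1 time point, two hours before surgery |
| Table 9.1 footnote 7, read literally | 2 (twice daily, day of surgery included) |
| Appendix III, day-of-surgery row | 2 open cells (morning and evening) |

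**Step 2. Is the open cell deliberate?** The diary has 13 rows (13 days to 1 day before surgery) + 2 rows for a delayed operation + 1 row for the day of surgery = 16 day rows. In all 16 the evening encorafenib cell is struck out and the evening binimetinib cell is open, so the last row repeats the 15 above it. A late operating slot does not explain this. Both drugs are due at the same two-hour point, so a late slot would need the evening encorafenib cell open as well.

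**Step 3. Dose count over the lead-in.** The day of surgery is counted as the last of the 10-14 days (assumption, following footnote 7). For a lead-in of d days the rule allows 2(d − 1) + 1 doses and the diary offers 2d cells.

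- d = 14: 2 × 13 + 1 = 27 doses against 2 × 14 = 28 cells.
- d = 10: 2 × 9 + 1 = 19 doses against 2 × 10 = 20 cells.
- Difference: 1 dose in either case.

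**Step 4. Size.** One dose is 45 mg, or three 15 mg tablets (Sections 4.3 and 6.2). Section 11.2 plans 6 surgical patients, so the ceiling is 6 × 1 = 6 doses. Section 4.1 replaces patients whose histology is not high-grade glioma; the documents do not say how many, and each could add one dose.

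**Step 5. Effect on the record.** If the open cell were counted as a missed dose, apparent compliance would be 27/28 = 96.4% or 19/20 = 95.0%. Both are well above the 80% that Section 10.0 gives as an example of inadequate compliance.

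**Step 6. Effect on results.** Table 9.2 schedules the pharmacokinetic blood after induction and after closure, the CSF before tumor disturbance and the frozen tumor samples during resection. An evening dose would normally come after all of them. Section 11.2 bases no clinical or trial decision on this cohort.

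**The case against.** The strongest reply is that this is a matter of tidying a form. The body text states the rule several times. The diary is titled as a pre-surgical one, the disputed row is tied to the two-hour time point, and no rows follow it. A blank cell is a place to record, not an order: the two delay rows, and the early rows of a 10-day patient, are also left blank in ordinary use. Footnote 7 opens by limiting itself to the pre-surgery period and points to Section 4.3. The binimetinib line of Table 9.1 has no entry under post-surgery, and Table 9.2 has no drug entry after closure. Patients are seen by study staff that day, bring the form and leftover pills to surgery, and undergo general anesthesia. The hemorrhage note names the eyes, gastrointestinal tract and lungs, not the operative site, and the protocol itself gives both drugs two hours before the incision. Finally, shading in the printed diary could have been lost when the PDF was read.

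Much of this stands: an unintended dose is unlikely, and the documents do not show what risk it would add. But none of it puts a stop instruction on the form the patient holds, and nothing in the diary sends the patient to Section 4.3. The strike-out marks survived in all 16 rows, so lost formatting is a weak explanation for the cell. The missing stop sentence and the wording of footnote 7 do not depend on layout at all.

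**Conclusion.** The concern holds as a minor inconsistency between a written rule and two places that should apply it. The rule gives one binimetinib dose on the day of surgery; the diary, and footnote 7 read literally, leave room for two. The size is at most one extra 45 mg dose per surgical patient, so at most 6 in the planned cohort plus replacements. That is a ceiling, not an expected number. It assumes that the day of surgery counts as one of the 10-14 lead-in days and that the diary layout was read correctly. The primary endpoint, the pharmacokinetic sampling and the trial's decisions are untouched. Correction is worthwhile because the form guides dosing around brain surgery and the change is very small.

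**What to change.** Keep the rule in Sections 4.1, 4.3 and 9.6.5 as it stands, and make three small changes to the two places that depart from it:

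1. In Appendix III, strike out the evening binimetinib cell on the day-of-surgery row, as is already done for encorafenib.
2. Add one sentence to the diary instructions: *Take no more of either drug after this dose until your study team tells you to restart.*
3. Reword the surgical-arm part of Table 9.1 footnote 7 to: *twice daily through the day before surgery, then a single dose two hours before surgery.*

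The cost is a short edit to the diary form and one to the footnote in the next amendment. Design, sampling and analysis do not change.
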